Follow-up and Attrition: Consistent with the parent study^{25,26} and our prior research with opioid-dependent patients^{23,24} we will collect detailed locator information, including cell phone numbers (for calls or texts), contact information for relatives and peers, and names and addresses of participants' "hang-outs." We will also, with permission of the participant, collect email addresses and social media contact information (e.g., facebook; Twitter) in order to contact the participant. When unable to contact participants via phone, the RAs will track the participants in the community through our successful and robust procedures for participant tracking. Thus, we expect to obtain follow-up rates of about 90%, consistent with our previous studies in Baltimore City with out-of-treatment opioid dependent individuals^{23,24,105} and the parent study.^{25,26} The PI and his staff have located over 90% of participants at 10-month follow-up for the first study of Interim Methadone, and at 12 months in both the parent study, and in the RCT of methadone for prisoners.³⁹

Measures: Figure 1 shows a schedule of the measures corresponding to each study aim.

Figure 1. Data Collection Schedule and Measures by Aim

Measures	Baseline	Follow-up
Aims 1-2: To compare IM + Patient Navigation v. IM alone v. Methadone Detoxification (Enhanced Treatment-as-Usual) on: treatment entry and retention, illicit opioids and cocaine use, DSM-5 criteria for opioid and cocaine use disorders; HIV-risk behaviors, criminal activity, arrest, and incarceration.		
Treatment Entry (self-report from Methadone Treatment Exposure form))		1 month
Enrolled in Treatment (self-report from Methadone Treatment Exposure form)*		3, 6, & 12-month
Illicit Opioid and Cocaine Use (ASI and urine drug testing)	◆	1,3, 6, & 12-month
DSM-V Criteria of opioid and cocaine use disorder (modified WMH CIDI)	◆	3- 6, and 12-month
Criminal Behavior (ASI)	◆	1,3, 6, & 12-month
Arrests and Incarcerations: Self report and criminal justice records	◆	12-month
HIV Risk Behavior (RAB)	◆	6, & 12-month
Overdose AE Form		1,3, 6, & 12-month
Methadone Treatment Exposure Questionnaire		1,3, 6, & 12-month
Quality of Life (WHOQOL-BREF)	◆	1,3, 6, & 12-month
Aim 3: To conduct a cost-benefit analysis of the relative costs of the three study Conditions		
Economic Form 90 (Health care utilization)	◆	3, 6, & 12-month
Substance Abuse Services Cost Analysis Program (SASCAP)		†

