Explanatory Variables. The predictor variables in all statistical models can be categorized as either Treatment Variables, Moderator Variables, or Control Variables.

Treatment Variables: There will be a single treatment variable with three conditions: Intervention Condition [IM+PN v. IM Alone v. Methadone Detoxification (ETAU)].

Moderator Variables: There will be a single moderator variable: Participant Gender.

Control Variables: Three additional predictor variables – participant age, prior methadone maintenance treatment (yes v. no), and self-reported cocaine use at baseline – will be included as “main effects” in all analyses in order to examine for potential differences in treatment outcome as a function of these three variables. (In the parent study: 56% had never previously been in MM treatment; and, self-reported cocaine use at baseline predicted lower treatment retention at 6 months).

Time: Finally, the “repeated factor” in the statistical analysis of all outcome variables measured repeatedly will be assessment Time point, which will allow for the evaluation of both *differential course and impact* of the interventions as a function of the “between-subjects” Treatment Condition factor. (For information regarding which outcome variables are measured at what assessment time points, see **Figure 1. Outcomes and Measures by Aim and Measures**, above).

Planned Contrasts: It is possible to construct two orthogonal, single-degree-of-freedom, planned contrasts that directly test **Hypothesis 1A** and **1B**, respectively. Contrast 1A will compare the two IM treatment conditions (IM+PN and IM Alone, pooled) to the Methadone Detoxification condition. Thus, this comparison directly addresses the question of the differential effectiveness of some form of IM treatment in comparison to a ‘minimally sufficient’ treatment-as-usual (methadone detoxification). Contrast 1B will compare the IM+PN condition to the IM alone condition. Hence, this comparison directly addresses the question of the relative

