Assuming $\alpha=.01$ and $N=300$, the resulting SAS GLIMMIX power estimates ($1 - \beta$) for the four planned contrasts X Time (see *Planned Contrasts*, above; for retained in treatment and arrest and incarceration, the effect of interest was necessarily the four planned contrasts themselves, as there was no Time effect for this outcome) associated with **Hypothesis 1A, 1B, 2A, and 2B** exceeded .81 in all cases, assuming “small” differences associated with each such effect, and even assuming an unstructured covariance matrix. For the set correlation approach, and in this case assuming $N=270$ due to attrition (see *Follow-up and Attrition*, above) in order to remain conservative, an effect size in the population associated with a Planned Contrast X Time for **Hypothesis 1A, 1B, 2A, and 2B** of $f^2=.048$ (.094 for retained in treatment and arrest and incarceration) would yield a power of .9 for that effect. [All 4 Planned Contrasts X Time for **Hypothesis 1A, 1B, 2A, and 2B** have the same degrees of freedom, so yield a common effect size.] The effect size involving the Time effect falls in the “small” range, while the effect size that does not include a Time effect falls in the “small-to-medium” range, with $f^2=.02$ considered a “small” effect and $f^2 = .15$ a “medium” effect.¹²¹

9. Process Evaluation.

9.a. Need for Process Data: Due to the key role of PN in this study for overcoming barriers associated with community re-entry (**Aim 1**), particularly for women (**Aim 2**), we will conduct a qualitative process evaluation that will examine PN experiences in detail.

9.b. Qualitative Sample Selection: Using purposive sampling, a subset of 32 participants (16 IM+PN and 16 IM alone) will be selected to complete semi-structured qualitative interviews. Participant selection will emphasize heterogeneity in order to examine the views and experiences from as diverse a sub-sample as possible and will include an equal number of men and women from each condition. The proposed sample size will ensure that saturation is likely to be achieved (i.e., bringing new participants into the study until the data set is complete, as indicated by data replication or redundancy) and should allow for the extraction of thick, rich data

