Months 1-5 of this proposed four-year project will be devoted to start-up activities, including confirming logistic arrangements, completing the PN manual with consultant [name], training staff, developing detailed procedures with MMP in the Detention Center and the community, obtaining OHRP approval, and finalizing the standard operating procedures.

Participant recruitment and delivery of interventions will begin in Month 6. Approximately four participants (2 male and 2 female) will be enrolled during each week in Months 6-28 yielding a total of 300 participants (100 participants per treatment condition). Follow-up assessments at 1-, 3-, 6-, and 12-months post-baseline will begin in study month 9, and end in study month 42. Although manuscript preparation will be ongoing throughout the study's data collection phase, the last five months of the project, Months 41-48, will be devoted to conducting the final follow-up interviews, data cleaning, obtaining the participant treatment and public safety records, and final outcome analyses and related manuscript preparation.

Dissemination Plan

We will continue to publish our findings in the scientific literature and to make presentations at recognized national and international meetings (see **Progress Report**, above). Locally, we will keep the Baltimore Behavioral Health Systems, the Baltimore City Health Department, the Baltimore-area MMP directors, and the Director of Maryland's Alcohol and Drug Abuse Administration and Department of Health and Mental Hygiene, and the Secretary of the Maryland Department of Public Safety and Correctional Services, up-to-date regarding the study and its implications. At the national level, we will work closely with CSAT's National Addiction Technology Transfer Centers, CSAT's Division of Pharmacologic Therapies to ensure dissemination of the study's progress and findings. The findings will also be shared with the National Association of State Alcohol and Drug Abuse Directors and the American Association for the Treatment of Opioid Dependence to make certain that the state substance abuse agencies and the nation's methadone providers are informed about the study, should it prove effective. Finally, the investigators will work closely with NIDA Notes staff in order to communicate findings to the field.

HUMAN SUBJECTS

Study Participants

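### The power stated for retention belongs to a different test from the one planned, and the claim of power above .81 for small differences fails for outcomes measured once, such as treatment entry

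*Combined protocol and SAP*

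**What the plan says.** The Power section, "Assuming $\alpha=.01$ and $N=300", reports GLIMMIX power above .81 for all four planned contrasts by Time, for differences it calls small. It excepts two outcomes, retention in treatment and arrest/incarceration. For these the contrast itself was powered, "as there was no Time effect for this outcome". A second calculation, by set correlation and "assuming $N=270$ due to attrition", gives the effect sizes for power .9: f² = .048 with Time, and .094 for the two excepted outcomes. The section takes f² = .02 as its benchmark for a small effect.

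Three other places bear on this:

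- **Figure 1.** The row "Enrolled in Treatment (self-report from Methadone Treatment Exposure form" is scheduled at 3, 6 and 12 months. The row "Treatment Entry (self-report from Methadone Treatment Exposure form" is scheduled at 1 month only. Measures for Aim 1 and 2 ties entry to the first 30 days after release.
- **Explanatory Variables, Time.** The repeated factor "in the statistical analysis of all outcome variables measured repeatedly will be assessment Time point".
- **Planned Contrasts.** Where there is a repeated factor, each contrast is examined by its interaction with Time, and at a single time point if that interaction is significant.

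**The concern.** Retention is powered as an outcome without Time, but its only defined measure has three time points, and the analysis text would test it with Time and Contrast by Time. A reader cannot tell which result will decide Hypotheses 1A and 1B for retention, and these tests can have very different power on the same data.

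Entry is the opposite case. It has one measurement, so it cannot have a Time effect, yet the exception does not name it. Read literally, entry falls under a power claim for an interaction that cannot be fitted. No outcome is designated primary, but entry and retention are the first-listed outcomes in Aim 1 and in Hypotheses 1A and 1B, and they are what patient navigation is meant to change.

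**Working it through.** **Inputs.** Alpha is .01; its sidedness is not stated, so I take it as two-sided. Project Timeline gives "yielding a total of 300 participants (100 participants per treatment condition". Follow-up and Attrition says "we expect to obtain follow-up rates of about 90" per cent, hence 270 in all and 90 per arm. The contrasts have one degree of freedom. The rationale for Hypothesis 1B cites entry rates of 14% to 50%.

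**1. The plan's own figures.** Power for a contrast with u = 1 comes from the noncentral F with λ = f²(u + v + 1). I take v = N − 9 (intercept, two for condition, gender, two for condition by gender, three control variables).

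- At N=270, v = 261, power .90 requires f² ≈ .057 (.056 to .058 across plausible model df). The plan states .094 without Time, at which this formula gives power .99. The stated figure does not reproduce, but the error is on the cautious side.
- The GLIMMIX result cannot be rebuilt, because the assumed rates and covariances are not given.

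**2. A small effect on a once-measured outcome** (f² = .02, u = 1, alpha .01).

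- N=300: v = 291, λ = .02 × 293 = 5.86, critical F = 6.72, power .43.
- N=270: v = 261, λ = .02 × 263 = 5.26, critical F = 6.73, power .38.
- Power .81 at N=300 needs f² ≈ .041, about twice the benchmark.
- At f² = .02, power reaches .81 with 600 independent observations, that is, two per participant. A once-measured outcome supplies one.

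**3. Treatment entry in percentage points** (Contrast 1B, 90 v 90, power .81). Solve

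d = (2.576 + .878) × √{[p₁(1 − p₁) + p₂(1 − p₂)]/90}, with p₂ = p₁ + d.

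- p₁ = .14: √[(.1204 + .2290)/90] = .0623, d = 21.5 points.
- p₁ = .30: √[(.2100 + .2479)/90] = .0713, d = 24.6 points.
- p₁ = .50: √[(.2500 + .1914)/90] = .0700, d = 24.2 points.

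A pooled-variance test adds about half a point. A 20-point gain has power of about .74 from 14% and .59 from 30% or 50%.

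**4. Does the choice of test matter for retention?** The documents give no enrolment rates over time and no within-person correlation, so this is an illustration on assumed values. It uses 90 per arm, correlation ρ = .3 to .7, and a Wald test on logits, where each arm's logit has variance 1/[n p(1 − p)] at each visit.

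| Assumed enrolment at 3/6/12 months | Averaged contrast | Contrast by Time (2 df) | 12 months alone |
|---|---|---|---|
| 70/60/50% v 50/40/30% | .87 to .67 | .01 | .56 |
| 70/55/40% v 40/35/30% | .87 to .67 | .26 to .67 | .12 |

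Check for row 1 at ρ = .5: the mean logit difference is .835, its variance is about .0958 × (1 + 2 × .5)/3 = .0638, z = 3.31, and power is Φ(3.31 − 2.58) ≈ .77. A steady 20-point benefit is therefore found quite often by the averaged contrast and almost never by Contrast by Time.

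**The case against.** The strongest defence is that retention was meant as a duration. The hypotheses speak of longer retention, the consent covers community methadone treatment data and admission and discharge dates from other public programmes, and Project Timeline schedules collection of treatment records. One duration per person would have no Time effect, and the Power section would then be right. This is feasible, but Measures and Figure 1 define no such variable; they name self-reported enrolment only. The mismatch stands until a duration is defined.

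Other parts of the defence succeed, and they bar several stronger readings that a reader might infer:

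- *Entry and retention have been swapped.* Nothing assigns entry a Time effect. The Planned Contrasts text uses Time only where there is a repeated factor, so entry already takes the plain contrast. Only the power statement omits it.
- *Entry has no power at all.* The .094 figure for effects without Time could be read across to entry. The plan does not do so, however, and the figure assumes a normal outcome while entry is binary.
- *The retention visit could be picked after seeing the data.* No section says that one visit will be chosen, and single-time-point tests are conditional on a significant interaction.
- *Retention power is overstated because of the mismatch.* This is not shown. The figure without Time (.094) is a larger required effect than the one with Time (.048).

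It is also fair to say that the plan sets no target difference for entry, so 22 to 25 points is not a shortfall against a stated aim. The f² = .02 result reaches every single-occasion contrast, including arrest and incarceration, so listing entry correctly would not cure it. The claim itself has to be restated.

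**Conclusion.** The point holds in two parts. First, the Power section and the analysis text give retention different tests, and the stated power does not belong to the planned one. This rests on the text alone. Second, power above .81 for small differences is not met for a once-measured outcome: it is about .43 at N=300 and .38 at N=270. This assumes that the section's f² = .02 benchmark is what small means in the GLIMMIX statement, that alpha is two-sided, and that the contrast has one degree of freedom; other model df move the figures by about .01. The entry differences of 22 to 25 points assume 90% follow-up and IM-alone rates within the 14% to 50% that the protocol cites. The retention table shows only that the choice of test matters; it does not estimate this trial's power.

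**What to change.** - **Retention.** Reconcile the Power section with Figure 1. Analyse enrolment at 3, 6 and 12 months as a repeated binary outcome in the planned mixed model. Name the planned contrast averaged over the three visits as the test, and report per-visit estimates with confidence intervals. If a single duration was meant, define it, with its data source and its handling of re-incarceration and loss to follow-up, and keep it without Time.
- **Entry.** List it with the single-occasion outcomes.
- **Power.** For single-occasion outcomes, replace the claim about small differences with detectable differences. For entry, Contrast 1B, 90 v 90, two-sided alpha .01 and power .81, that is about 22 to 25 percentage points for assumed IM-alone rates of 14% to 50%. State the assumed rates and correlations behind the retention figure.

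The cost is wording and a rerun of the power calculation, with no new data or visits. The downside is that the stated power becomes less favourable. Averaging over visits is one reasonable choice; a defined duration would resolve the mismatch equally well.

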However, the PN literature shows that women respond well to this intervention.^{116,117} Therefore, although we anticipate that women will have poorer outcomes than men in the IM alone and detoxification conditions, we hypothesize that women will respond better than men to IM+PN.

Analyses for Aims 1 and 2.

Intent-to-Treat Approach. All analyses will be conducted on available study-related data from all participants (based on their random assignment to treatment condition), regardless of whether or when they drop out of treatment.

Guiding Principle. Although the description of the statistical approach that follows is more in line with the language associated with a ‘traditional’ superiority trial, we endorse the “sensible formulation of the significance test” proposed by Jones and Tukey.¹¹⁸ They outline an approach to significance testing that focuses not on the rejection of a null hypothesis, but on determining whether the data favor a determination of superiority or inferiority. As part of their approach, they suggest reporting not only a test statistic and its associated probability value but also a confidence interval and an effect size related to the determination of any difference. It would be our intention in reporting our results to adhere to Jones and Tukey’s suggestions.

Outcome Variables. Outcome variables will be of three distinct types: 1) dichotomous variables (e.g., entry into treatment, illicit opioid and cocaine urine test results, meeting DSM-5 opioid and cocaine dependence criteria), assumed to follow a binomial distribution; 2) discrete random variables (e.g., number of days of heroin and cocaine use and criminal behavior in the past 30 days), assumed to follow a Poisson distribution; and, 3) continuous random variables (e.g., HIV Risk scale scores), assumed to follow a normal distribution. All distributional assumptions will be evaluated prior to the conduct of all analyses, and if such assumptions are not met, assumptions will be modified and statistical methods chosen accordingly, and/or outcome measures transformed appropriately. For example, it may be necessary to allow for under- or over-dispersion in the logistic and Poisson regression analyses; or a negative binomial model may be more appropriate for the count variables. [In the case of transforming an outcome variable, preference will be given to a transformation that permits clearer clinical interpretation of findings].

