effectiveness of the adding PN to IM treatment. Similarly, it is possible to construct two orthogonal, single-degree-of-freedom, planned contrasts that directly test **Hypothesis 2A** and **2B**, respectively. Contrast 2A will compare males and females in the IM+PN condition. Hence, this comparison directly addresses the question of the differential effectiveness of IM+PN treatment for males and females. Contrast 2B will compare males and females in the IM Alone and Methadone Detoxification conditions, pooled. Thus, this comparison directly addresses the question of the differential effectiveness of non-PN treatments for males and females. Given that both the course and impact of treatment are important to evaluate, planned contrasts can be examined both as each interacts with the “repeated factor” of Time (when there is a repeated factor), and as a “simple effect” at a given time point, in the event either Contrast X Time interaction effect proves to be significant.

AIM 3: To conduct a focused cost-effectiveness and cost-benefit study of the three treatment conditions

HYPOTHESIS 3a (Cost Hypothesis). IM alone will have greater treatment costs per person than detoxification. Furthermore, IM+PN will have greater treatment costs per person than IM alone.

HYPOTHESIS 3b (Cost-Effectiveness Hypothesis). IM+PN will yield better outcomes relative to the IM alone which in turn will yield better outcomes than detoxification in terms of higher rates of treatment entry and longer retention in treatment, and greater reductions in illicit opioid and cocaine use, decreased likelihood of meeting DSM-5 criteria for opioid and cocaine use disorders, decreased HIV risk behavior, and decreased criminal behavior, arrest, and incarceration. The better outcomes for IM+PN justify the greater costs of IM+PN compared to IM alone, making IM+PN cost effective compared to IM alone.

HYPOTHESIS 3c (Cost-Benefit Hypothesis). IM alone will yield greater economic benefit in terms of criminal activity, health care utilization, and employment in the 12-month post-release period relative to its costs relative to the detoxification condition. Furthermore, IM+PN will yield greater economic benefits than IM alone.

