Rationale: By design, it is expected that IM+PN will require additional resources (e.g., labor, transportation expenses) relative to IM Alone and detoxification only due to the inclusion of PNers who are trained to facilitate enrollment in drug treatment for the participant as well as provide assistance in the early months of treatment. However, this additional case support is expected to yield better treatment entry and retention and, subsequently, improved outcomes. If these benefits exceed the additional costs, we would expect to find IM + PN to be cost-effective and cost-beneficial relative to the other 2 treatment conditions.

Statistical Method. A Generalized Linear Mixed Model (GLiMM) will be used to conduct all analyses.

Power. Stroup^{119,120} has outlined a four-step procedure to estimate power for general linear mixed models, which can also be applied to generalized linear mixed models, and this procedure was followed to estimate power for the proposed study. From a more rudimentary and slightly less accurate perspective, assuming the primary outcome measures follow a normal distribution rather than Poisson or binomial distributions, power calculations based on the set correlation method^{121,122} can be used to calculate effect sizes for desired power, including under the extremely conservative assumption that no other effect in the model is significant (with the resulting effect size estimates likely to be slight underestimates). For the sake of completeness, power calculations employ both perspectives.

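### The stated power of .9 at f²=.094 does not fit the single-df contrasts it describes: at N=270 and alpha .01 their power is about .99, and .9 needs only about .056 (two-sided) or .049 (one-sided)

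*Combined protocol and SAP*

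**What the plan says.** The Power section gives two calculations. The first uses SAS GLIMMIX with alpha .01 and N=300. It reports that power for the four planned contrasts by Time "exceeded .81 in all cases", for differences described as small but not given a number. The second is the set correlation method, used "assuming the primary outcome measures follow a normal distribution rather than Poisson or binomial distributions". It takes N=270, in line with the Follow-up and Attrition paragraph, where "we expect to obtain follow-up rates of about 90"%.

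The set correlation sentence attaches power .9 to two effect sizes: f²=.048 for a contrast by Time, and .094 for outcomes without Time. The second reads "094 for retained in treatment and arrest and incarceration) would yield a power of .9 for that effect" (the quotation starts after the decimal point). For those outcomes, retention and arrest and incarceration, the section says that the effect of interest is the planned contrasts themselves, "as there was no Time effect for this outcome".

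The Planned Contrasts text describes each pair (1A and 1B, then 2A and 2B) as "two orthogonal, single-degree-of-freedom, planned contrasts that directly test" the corresponding hypotheses. The Power section adds that the four contrasts by Time share the same degrees of freedom, but gives no number. It then grades the two effect sizes. The sentence beginning "The effect size involving the Time effect falls in the" puts .048 in the small range and .094 in the small-to-medium range, against benchmarks of .02 (small) and .15 (medium).

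**The concern.** Once the effect is a single-df contrast and the method, N and alpha are fixed, power at a given f² follows apart from sidedness. The plan fixes all of these except sidedness, and sidedness hardly matters at .094. The stated .9 can therefore be checked directly, and an f² of .094 looks too large for it.

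The Power section is the plan's only quantitative justification for its sample size. If .094 is wrong for the contrasts, readers are given the wrong detectable effect for retention, which stands near the front of Hypotheses 1A and 1B, and for arrest and incarceration. They are also told that these outcomes need about twice the effect size of the repeated outcomes (.094/.048 = 1.96), a comparison that rests on the same figure.

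**Working it through.** **Inputs.** Alpha .01 comes from the opening of the power paragraph. It is stated with the GLIMMIX calculation and assumed here to carry over. N=270 and f²=.094 come from the set correlation sentence. Numerator df u=1 comes from Planned Contrasts. Sidedness is not stated, so both are shown.

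**Formula.** Two-sided power is the probability that a noncentral F with u and v df and noncentrality λ exceeds the central critical value, where λ = f²(u+v+1) and v = N−u−1, so λ = f²N. One-sided power uses a noncentral t with noncentrality √(f²N).

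**Trying to reproduce .9.**
- λ = .094 × 270 = 25.38; √25.38 = 5.038; v = 268.
- Two-sided: the critical F is 6.730 and power is .992. Normal check: Φ(5.038 − 2.576) = .993.
- One-sided: the critical t is 2.340 and power is .996.

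The stated .9 is not reproduced.

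**f² that gives .9 with one df.**
- Two-sided: .0558. Normal check: (2.576 + 1.282)²/270 = 14.88/270 = .0551.
- One-sided: .0487. Normal check: (2.326 + 1.282)²/270 = 13.02/270 = .0482.

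**Other single-df readings at f²=.094, two-sided.** Alpha .05 gives .999. Alpha .005, .0025 and .00125 give .986, .976 and .961. N=300 gives .997. Two arms only (N=180) gives .933, and one arm (N=90) gives .608. None gives .9.

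**More numerator df, N=270, alpha .01.**

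| df | power at .094 | f² for power .9 |
|---|---|---|
| 1 | .992 | .0558 |
| 2 | .982 | .0657 |
| 3 | .969 | .0728 |
| 4 | .954 | .0788 |
| 5 | .938 | .0839 |
| 6 | .922 | .0886 |
| 7 | .904 | .0930 |
| 8 | .887 | .0970 |

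Only 7 to 8 df comes near .9.

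**What the difference means.** Assume equal allocation and gender balance in the 270. The groups are then 180 v 90 (1A), 90 v 90 (1B and 2B) and 45 v 45 (2A), and d = √(f² × 270 × (1/n₁ + 1/n₂)). At .094, d is .65, .75 and 1.06. At .0558, d is .50, .58 and .82.

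**The two neighbouring figures.**
- f²=.048 at N=270, two-sided, persons as the unit: .84, .75, .69 and .63 for 1 to 4 df. A one-sided 1-df test gives .895. Counting 540 independent rows (two per person), two-sided, gives .994, .985, .974 and .961 for 1 to 4 df, and .919 and .904 for 7 and 8 df.
- The GLIMMIX claim, illustrated by a two-sided 1-df contrast without Time at N=300: .44 at f²=.02 and .88 at f²=.048. Power .81 needs about .040.

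**The case against.** The strongest reply is that .094 may be a correct answer to a different question. At 7 to 8 df it gives .904 to .887 with 270 units, and .048 gives .919 to .904 with 540 rows, so one multi-df test could roughly explain both figures. The explanatory variables listed in the plan also add up to 8 df: condition 2, gender 1, their interaction 2, controls 3. The fault may therefore be a misapplied or undeclared df rather than a slip in calculation. This stands as a plausible source, but only as an inference. The plan names no such test for these outcomes, and an omnibus figure cannot be reported as the power of a single-df contrast. It does mean that the sponsor should be free to name the test instead of simply replacing the number.

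Second, the consequence is limited. The section itself treats set correlation as the rougher of its two methods, and the error is conservative. The Guiding Principle paragraph turns attention away from rejecting a null, "but on determining whether the data favor a determination of superiority or inferiority", and promises confidence intervals and effect sizes. All of this stands. It limits the harm, but the stated figure still needs correcting.

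Third, a reader might infer that the trial is underpowered, or that .048 and the .81 claim are also wrong. The documents support neither inference. The .094 error runs the other way. For .048, some choices the text leaves open give about .9 and others do not. For the .81 claim, the result depends on which effect was meant by small, since the paragraph applies that label to both .02 and .048. These are unstated inputs, not demonstrated errors.

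The premise that retention has no Time effect is taken from the plan as it stands, although Figure 1 schedules enrolment in treatment at 3, 6 and 12 months.

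**Conclusion.** The point holds for .094. For the single-df contrasts the plan defines, at N=270 and alpha .01, power at f²=.094 is about .99, not .9, and .9 needs about .056 two-sided or .049 one-sided. The stated effect is larger than required by a factor of about 1.7 (.094/.056) or 1.9 (.094/.049). No single-df reading tried, and no test of 2 to 6 df at N=270, brings it to .9.

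This rests on the set correlation method under normality, as the plan states it, and on alpha .01 applying to that sentence. At alpha .05 the gap would be wider. The direction is conservative: N=300 is not called into question, and no loss of power is shown.

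The .048 figure and the GLIMMIX claim are unverifiable as written, and nothing more is concluded about them.

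**What to change.** 1. For the single-df contrasts without Time, restate the effect size for power .9 at N=270 as f²=.056 if the tests are two-sided, or .049 if one-sided. Revise the small-to-medium comparison, since the value is then close to the .048 that the paragraph calls small.
2. If .094 came from a multi-df test, name that test and its df, and do not attribute the figure to the planned contrasts.
3. In the same edit, state the sidedness, numerator df and unit (persons or repeated rows) behind .048, and give the numeric effects used in GLIMMIX for the .81 claim.

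The cost is wording only, with no change to sample size, visits or data. Item 1 can be done from the plan's own inputs once sidedness is declared. Items 2 and 3 need the sponsor's original power inputs.
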